#### 11.3.5.8.3. Clinical Laboratory Evaluations

Clinical laboratory data (clinical chemistry and haematology) will be summarised by the mean, median standard deviation, minimum and maximum values by treatment group and time point.

Laboratory data will also be evaluated by tabulating the number and percentage of subjects in each treatment group with values outside specified threshold values of clinical concern. (These may include values outside of the normal range, outer range of clinical concern, and other values of clinical concern.) These safety analyses will be defined in the analysis plan as appropriate.

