#### 6.2.2. Haematology and clinical chemistry

Due to the location of the study sites, the transit time required for shipment of samples and logistical constraints of cold-chain storage, haematology and clinical chemistry tests will be conducted by local laboratories for this study, rather than a central laboratory.

Clinical chemistry blood samples will be taken on days 0 (pre-dose), 3, 7 and 42. Samples should only be taken on day 14 or 28 if the previous results were abnormal. Clinical chemistry tests may be performed at the physician's discretion at any time on unscheduled follow-up visits.

Clinical chemistry tests to include: serum creatinine, serum total and indirect bilirubin, serum aspartate aminotransferase (AST) and serum alanine aminotransferase (ALT).

Haematology blood samples will be taken on days 0 (screening), 1, 2, 3, 7, 14, 28 and 42. Samples taken on days 0, 1 and 2 should be taken **before** dosing. Haematology tests may be performed at the physician's discretion at any time on unscheduled follow-up visits. Haematology tests to include: haemoglobin, haematocrit, reticulocyte count (% of red blood cells and absolute count calculated against red blood cells), red blood cell count, white blood cell count, platelet count, methaemoglobin when available.

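### Day 14 and day 28 chemistry is drawn only after an abnormal earlier result, yet the protocol summarises it by arm and time point as if all children were sampled

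*Protocol*

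**What the plan says.** Protocol section 6.2.2 sets the universal chemistry schedule: "Clinical chemistry blood samples will be taken on days 0 (pre-dose), 3, 7 and 42". For the two visits in between it says: "Samples should only be taken on day 14 or 28 if the previous results were abnormal". A footnote to the Time and Events Table in Appendix 1 repeats the restriction. Neither place says which earlier visit or which analyte makes a child count as abnormal. The panel is creatinine, total and indirect bilirubin, AST and ALT.

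Haematology has no such restriction: "Haematology blood samples will be taken on days 0 (screening), 1, 2, 3, 7, 14, 28 and 42". It includes haemoglobin, haematocrit and reticulocytes.

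Section 11.3.5.8.3 treats chemistry and haematology together. Both are to be "summarised by the mean, median standard deviation, minimum and maximum values by treatment group and time point". A second table gives the "number and percentage of subjects in each treatment group with values outside specified threshold values of clinical concern"; neither the visit nor the denominator is stated, and the section leaves the definition of these analyses to the analysis plan. Section 11.3.5.2 says that ITT summaries are made without filling in missing safety data.

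**The concern.** A table by arm and visit is normally read as a comparison of randomised groups. On days 14 and 28 the chemistry rows would not be one. A child enters those rows only after an abnormal result measured after randomisation, and treatment may influence that result. If one drug produces more mild abnormalities by day 7, its day 14 row contains more children who were only slightly abnormal, while the other arm's row keeps fewer and more extreme ones. The summary then favours the arm with the wider spread of mild abnormality.

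Laboratory tests by treatment group are a stated safety endpoint (section 3.2, safety endpoints), and section 11.2.2 gives additional CDA safety data as the reason for 2:1 allocation. A misleading row for bilirubin, transaminases or creatinine therefore sits in a part of the report that will be read closely. Section 11.3.5.8.4 also summarises laboratory data by arm and G6PD status; any by-visit version of that table would carry the same selection into smaller groups.

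**Working it through.** The protocol states no figure to reproduce here. The first step compares its rules; the second is an illustration on assumed inputs.

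**1. The rules side by side**

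| Laboratory data | Days 0, 3, 7, 42 | Days 14, 28 | Summary rule (11.3.5.8.3) |
|---|---|---|---|
| Chemistry | all children | only after an abnormal earlier result | by arm and time point |
| Haematology | all children | all children | by arm and time point |

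Missing safety values are not replaced, so a child not sampled on day 14 or 28 drops out of that row. Followed literally, the text gives a mean over the selected children, labelled as an arm.

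**2. How large the distortion could be**

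Assumptions, none from the protocol: the analyte is normal in SD units with comparator mean 0; a child is sampled on day 14 if the day 7 value exceeds a cut-off c; the day 7 to day 14 correlation is r; CDA shifts the mean by d7 on day 7 and d14 on day 14. Randomised numbers are 930 and 465 (section 5.1), taken as all attending.

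Let L(c) = φ(c) / [1 − Φ(c)], the mean of a standard normal above c. Then:

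- comparator mean among those sampled = r × L(c)
- CDA mean among those sampled = d14 + r × L(c − d7)
- apparent difference = d14 − r × [L(c) − L(c − d7)]

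*(a) No true day 14 difference; 5% of comparator and 15% of CDA children abnormal on day 7; r = 0.5.* L is 2.06 at 5% and 1.55 at 15%. The sampled means are 0.5 × 2.06 = 1.03 SD (comparator) and 0.5 × 1.55 = 0.78 SD (CDA), an apparent 0.25 SD in favour of CDA. About 0.15 × 930 = 140 CDA and 0.05 × 465 = 23 comparator children are sampled. With 10% to 20% abnormal on CDA and r of 0.5 to 0.7, the range is 0.5 × (2.06 − 1.75) = 0.15 to 0.7 × (2.06 − 1.40) = 0.46 SD.

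*(b) Persistent CDA excess, d7 = d14 = 0.40.*
- c = 1.0: 0.40 − r × (1.525 − 1.215)
- c = 1.645: 0.40 − r × (2.063 − 1.725)

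*(c) Mostly resolved excess, d7 = 0.60, d14 = 0.10.*
- c = 1.0: 0.10 − r × (1.525 − 1.069)
- c = 1.645: 0.10 − r × (2.063 − 1.561)

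| Apparent day 14 difference (SD) | r = 0.3 | r = 0.5 | r = 0.7 | r = 0.9 |
|---|---|---|---|---|
| (b) true +0.40, c = 1.0 | +0.31 | +0.24 | +0.18 | +0.12 |
| (b) true +0.40, c = 1.645 | +0.30 | +0.23 | +0.16 | +0.10 |
| (c) true +0.10, c = 1.0 | −0.04 | −0.13 | −0.22 | −0.31 |
| (c) true +0.10, c = 1.645 | −0.05 | −0.15 | −0.25 | −0.35 |

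A simulation with 2,000,000 children per arm gave the same values to within about 0.01 SD. At c = 1.645, 5% of comparator children (about 23) and 11% to 15% of CDA children (about 99 to 138) are sampled. At c = 1.0 the shares are 16% (about 74) and 27% to 34% (about 255 to 320).

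**The case against.** The strongest reply is that this is table layout, which belongs in an analysis plan that is not at hand. That holds for the threshold table, whose details the protocol defers. It does not hold for the descriptive summary: the protocol itself fixes arm and time point as its layout, and an analysis plan that follows it reproduces the problem.

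A reader might infer that a haemolysis signal could be hidden. The documents do not support this. Haemoglobin, haematocrit and reticulocytes are scheduled for every child on days 14 and 28; section 10.2 makes haemoglobin falls of 40% or more, transfusions and values below 5 g/dL serious adverse events; and section 11.3.5.8.2 plans a separate table of haematological adverse events. Bilirubin is the only haemolysis-related analyte affected.

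A reader might also infer that a liver or renal signal would vanish. An arm difference large enough to distort selection should already show on day 7, when all children are sampled. In illustration (a), 15% against 5% abnormal means a day 7 difference of 1.645 − 1.036 = 0.61 SD. Its standard error is √(1/930 + 1/465) = 0.057 SD, so it stands more than 10 standard errors from zero. The spurious 0.25 SD on day 14 has a standard error of about 0.2 SD. Days 3 and 42 are unselected too.

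Reversal appears only in the scenario where most of the day 7 effect has gone by day 14; a persistent excess shrinks but keeps its sign throughout. Nor does the text say that threshold percentages are inflated: that would need a by-visit layout with sampled children as denominator, and neither is written. Finally, no test, margin or stopping rule in the protocol uses these means. All of this stands, and it limits the size of the point. None of it makes the day 14 and 28 chemistry rows valid arm comparisons.

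**Conclusion.** The point holds as a flaw in a descriptive safety table. The sampling rule and the summary rule, both in the protocol, together give day 14 and 28 chemistry figures for children selected on a post-randomisation result. That conclusion rests on the text alone.

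The size of the distortion rests wholly on assumptions (normality, cut-off, correlation, size of the CDA shift). Within them, a persistent 0.40 SD excess is attenuated to 0.10 to 0.31 SD, and an excess that has mostly resolved changes sign. The affected analytes are creatinine, bilirubin, AST and ALT at two visits; red-cell parameters and the other chemistry visits are not affected. The change is worth making because it is cheap and removes a comparison that would mislead, not because a safety conclusion hangs on it.

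**What to change.** In section 11.3.5.8.3:

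- Limit by-arm, by-visit summaries of chemistry to days 0, 3, 7 and 42. Leave haematology as planned.
- Report day 14, day 28 and unscheduled chemistry as follow-up of abnormal values: number sampled per arm, and number resolved or persisting.
- Tabulate threshold exceedances as the worst post-baseline value per subject, with all ITT children in the arm as denominator.

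The cost is analysis wording and table shells, with no extra blood samples. The downside is that no arm means for chemistry are shown for days 14 and 28.

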#### 11.3.5.8.4. G6PD Evaluations

The proportion of subjects with G6PD deficiency will be reported. Clinical laboratory data will be summarised by treatment group and G6PD status.

#### 11.3.5.9. Pharmacokinetic Analyses

Plasma concentration-time data for DDS, CPG, CCG, ART and DHA will be tabulated for each subject receiving CDA. Population pharmacokinetic methods will be performed using software such as NONMEM or other currently acceptable methods to assess the pharmacokinetics of CDA components, if data are appropriate. To support the population PK analysis, the data from this study may be combined with data from other studies. Mean population PK parameters will be assessed taking into account demographic variables (such as weight, age, gender), and concomitant medications. If data permit, the relationship between CDA component concentrations and selected adverse events will be explored.

# 12. STUDY CONDUCT CONSIDERATIONS

# 12.1. Regulatory and Ethical Considerations, Including the Informed Consent Process

GSK will obtain favorable opinion/approval to conduct the study from the appropriate regulatory agency in accordance with any applicable country-specific regulatory requirements prior to a site initiating the study in that country.

The study will be conducted in accordance with all applicable regulatory requirements.

The study will also be conducted in accordance with "good clinical practice" (GCP), all applicable subject privacy requirements, and, the guiding principles of the Declaration of Helsinki. This includes, but is not limited to, the following:

- IEC/IRB review and favorable opinion/approval to conduct the study and of any subsequent relevant amended documents
- Subject informed consent
- Investigator reporting requirements

GSK will provide full details of the above either verbally, in writing or both.

Written informed consent will be obtained for each subject before he or she can participate in the study.

# 12.2. Quality Control (Study Monitoring)

In accordance with applicable regulations, GCP, and GSK procedures, GSK monitors will contact the site prior to the start of the study to review with the site staff the protocol, study requirements, and their responsibilities to satisfy regulatory, ethical, and GSK requirements. When reviewing data collection procedures, the discussion will also include identification, agreement and documentation of data items for which the eCRF will serve as the source document.

GSK will monitor the study consistent with the demands of the study and site activity to verify that the:

- Data are authentic, accurate, and complete.
- Safety and rights of subjects are being protected.
- Study is conducted in accordance with the currently approved protocol and any other study agreements, GCP, and all applicable regulatory requirements.

The investigator and the head of the medical institution (where applicable) agrees to allow the monitor direct access to all relevant documents.

# 12.3. Quality Assurance

To ensure compliance with GCP and all applicable regulatory requirements, GSK may conduct a quality assurance audit. Regulatory agencies may also conduct a regulatory inspection of this study. Such audits/inspections can occur at any time during or after completion of the study. If an audit or inspection occurs, the investigator and institution agree to allow the auditor/inspector direct access to all relevant documents and to allocate his/her time and the time of his/her staff to the auditor/inspector to discuss findings and any relevant issues.

# 12.4. Study and Site Closure

Upon completion or premature discontinuation of the study, the monitor will conduct site closure activities with the investigator or site staff, as appropriate, in accordance with applicable regulations, GCP, and GSK procedures.

In addition, GSK reserves the right to temporarily suspend or prematurely discontinue this study at any time for reasons including, but not limited to, safety or ethical issues or severe non-compliance. For multicenter studies, this can occur at one or more or at all sites. If GSK determines such action is needed, GSK will discuss this with the investigator or the head of the medical institution (where applicable), including the reasons for taking such action, at that time. When feasible, GSK will provide advance notification to the investigator or the head of the medical institution, where applicable, of the impending action prior to it taking effect.

GSK will promptly inform all other investigators or the head of the medical institution (where applicable), and/or institutions conducting the study if the study is suspended or terminated for safety reasons. GSK will also promptly inform the regulatory authorities of the suspension or termination of the study and the reason(s) for the action. If required by applicable regulations, the investigator or the head of the medical institution (where applicable) must inform the IEC/IRB promptly and provide the reason for the suspension or termination.

# 12.5. Records Retention

Following closure of the study, the investigator or the head of the medical institution (where applicable) must maintain all site study records, except for those required by local regulations to be maintained by someone else, in a safe and secure location. The records must be maintained to allow easy and timely retrieval, when needed (e.g., audit or inspection), and, whenever feasible, to allow any subsequent review of data in conjunction with assessment of the facility, supporting systems, and staff. Where permitted by local laws/regulations or institutional policy, some or all of these records can be maintained in a format other than hard copy (e.g., microfiche, scanned, electronic); however, caution needs to be exercised before such action is taken. The investigator must assure that all reproductions are legible and are a true and accurate copy of the original, and meet accessibility and retrieval standards, including re-generating a hard copy, if required. Furthermore, the investigator must ensure there is an acceptable

back-up of these reproductions and that an acceptable quality control process exists for making these reproductions.

GSK will inform the investigator of the time period for retaining these records to comply with all applicable regulatory requirements. The minimum retention time will meet the strictest standard applicable to that site for the study, as dictated by any institutional requirements or local laws or regulations, or GSK standards/procedures; otherwise, the retention period will default to 15 years.

The investigator must notify GSK of any changes in the archival arrangements, including, but not limited to, the following: archival at an off-site facility, transfer of ownership of the records in the event the investigator leaves the site.

# 12.6. **Provision of Study Results and Information to Investigators**

When required by applicable regulations, the investigator signatory for the clinical study report will be determined at the time the report is written. When the clinical study report is completed, GSK will provide the investigator with a full summary of the study results. In addition, the investigator will be given reasonable access to review the relevant statistical tables, figures, and reports and will be able to review the results for the entire study at a GSK site or other mutually agreeable location.

Information on the progress of the study will be provided at intervals though newsletters and verbal presentations, so that all those involved in the study including study subjects can be kept fully informed. On completion of the study, in addition to the publication of data in the scientific literature, information on the outcome will be provided to subjects and to their communities in an appropriate manner (for example through the local media, through workshops or by direct contact with the subjects). Policy makers will be informed through the normal scientific channels, and local regulatory authorities will be provided with a summary of the outcomes of the study.

GSK will provide the investigator with the randomization codes for their site after the statistical analysis for the entire study has been completed.

# 12.7. Data Management

The data collection tool for this study will be GSK-defined electronic case report forms (eCRFs). In all cases, subject initials will not be collected nor transmitted to GSK. Subject data necessary for analysis and reporting will be entered/transmitted into a validated database or data system. Clinical data management will be performed in accordance with applicable GSK standards and data cleaning procedures.

# 12.8. Independent Data Monitoring Committee (IDMC)

An IDMC will be utilized during the conduct of this study. An IDMC is generally assembled when there are significant safety or efficacy issues that warrant external objective medical and/or statistical review in order to protect the ethical and safety interests of subjects and to protect the scientific validity of the study. The schedule of any planned interim analysis and the analysis plan for IDMC review is described in the charter. A copy of the IDMC charter is available from GSK upon request.

# Appendices

# Appendix 1: Time and Events Table

Changes have been made to the time & events table to reflect the modification of the assessment times, however the table has not been reproduced here to conserve space.

See next page

#### GM2005/00186/05 SB-714703/005

Assessment day		Day 0		Day 1	Day 2	Day 3	Day 4	Day 5	Day 6	Day 7	Day 14	Day 28	Day 42	Extra visit
Time (hr)	screening	Pre-dose	0	24	48	72								
Procedure														
Obtain informed consent from														1
parent / guardian and assent from	х													
child.														
Weigh subject, record length or														
height, collect demography data	Х													
Clinical assessment	Х	Х	Х	Х	Х	Х				Х	Х	Х	Х	Х
Record medical history	Х													
			X (every	X  (every	X  (every									
Tympanic temperature measured	Х	Х	8hrs)	8hrs)	8hrs)	Х				Х	Х	Х	Х	Х
Urine test for CQ	Х		011107	01110)	01110)									
Thumbprick - blood slide for			X (every	X  (every	X  (every									
parasite count (10ul)	Х	Х	8hrs)	8hrs)	8hrs)	Х				Х	Х	Х	х	Х
F ====== ( + = ==)			01115)	01115)	01115)									
Thumbprick - blood sample to filter		х								х	х	х	х	х
paper for parasite PCR (2 drops)		Λ								~	~	~	~	~
Venous blood sample for														
haematology (2ml)	Х			X 	X 	Х				Х	Х	Х	Х	(X) 
Venus blood sample for clinical														
chemistry (2ml)		Х				Х				Х	(X) 	(X) 	Х	(X) 
Serum pregnancy test  (4 drops)	Х													
Urine pregnancy test  (4 drops)													Х	
Blood sample for human G6PD														
PCR (10ul)		Х												
G6PD phenotype test (aliquot from		X												
haematology sample)		Х										(X) 		
Population PK sampling (2ml)			X 7	X 7	X 7					X 7				
Study drug administration (twice										~~~~				
daily dosing)			X 	х	х									
Field worker home visit							Х	Х	Х					
Concomitant medication recorded	Х	Х	Х	х	х	Х				Х	Х	Х	Х	Х
AE and SAE reporting	Х	Х	Х	Х	Х	Х				Х	Х	Х	Х	Х
Rescue medication if treatment														
failure			Х	Х	х	Х				х	х	х	Х	х

1. Including pre-dose assessments on days 1 and 2

2. Day 1 and 2 assessment should be before the first dose each day

3. At clinician's discretion

Samples should only be taken on day 14 or 28 if the previous results were abnormal.
 Female subjects of child-bearing potential. Serum day 0, urine day 42 or on early withdrawal

6. Repeat phenotype test if drop in haemoglobin of 40% or greater from baseline (screening) once Hb has recovered, or if day 0 retic levels were high

7. Up to five blood samples for population PK analysis will be collected from each subject. These samples will be collected within varying time windows: 0.25-0.5h, 1-3h, 4-8h, 12-24h and day 7

8. Second dose day 0 should be ~8hrs after first dose.

# Appendix 2: Country Specific Requirements

None.

# Appendix 3: Dosing of study drugs

# CDA

CDA tablets will be made in two sizes, to facilitate dosing of small children and infants:

CDA 12:15:24 tablets will contain 12mg CPG, 15mg DDS and 24mg artesunate.

CDA 60:75:120 tablets will contain 60mg CPG, 75 mg DDS and 120mg artesunate.

3-dose course: The following number of tablets should be taken at initial diagnosis after randomization, then once daily for the following two days.

12:15:24 CDA tablets									
No. of tablets	min weight	max weight	max mg/kg CPG	min mg/kg CPG	max mg/kg DDS	min mg/kg DDS	max mg/kg ART	min mg/kg ART	
1.0	5.00	<7	2.40	1.74	3.00	2.17	4.80	3.48	
1.5	7.00	<10	2.57	1.82	3.21	2.27	5.14	3.64	
2.0	10.00	<13	2.40	1.86	3.00	2.33	4.80	3.72	
60:75:120	CDA table	ts	1	1	T	1	1		
No. of tablets	min weight	max weight	max mg/kg CPG	min mg/kg CPG	max mg/kg DDS	min mg/kg DDS	max mg/kg ART	min mg/kg ART	
0.5	13.00	<19	2.31	1.59	2.88	1.98	4.62	3.17	
1.0	19.00	<31	3.16	1.94	3.95	2.43	6.32	3.88	
1.5	31.00	<46	2.90	1.96	3.63	2.45	5.81	3.92	
2.0	46.00	-	2.61		3.26	-	5.22	-	

#### Artemether-lumefantrine (Coartem)

Each tablet contains 20mg artemether and 120mg lumefantrine.

6-dose course: The following number of tablets should be taken at initial diagnosis after randomisation, then 8 hours after initial dose, and twice daily for the following two days.

- 5 <15kg 1 tablet
- 15 <25kg 2 tablets
- 25 <35kg 3 tablets
- $\geq$  35kg 4 tablets

# Appendix 5: Protocol Amendment 1 changes

#### Changes in Protocol amendment No.1.

This protocol amendment applies to Ghana only.

At the request of the IEC for the Kintampo site, all investigators and their collaborators need to be listed in the protocol.

The following investigators and collaborators will therefore be captured in Appendix 4.

